Alcohol's Effect on Neurophysiological and Psychophysiological Arousal. Low to moderate alcohol exposure has been shown to lead to neurophysiological and psychophysiological responses consistent with increased arousal. Although alcohol is considered a pharmacological depressant, during the absorption phase, also known as the ascending limb of intoxication, and at peak Blood Alcohol Concentration (BAC), alcohol is actually arousing (Levenson, Sher, Newman, & Newlin, 1980; Schwartz et al., 1981). Electroencephalography (EEG) investigations of EEG frequencies aligned with a continuum of consciousness have found that during the ascending limb of intoxication, and at peak Blood Alcohol Concentration (BAC), alcohol is associated with increases in fast frequencies (beta and alpha; alertness and vigilance, and wakefulness, respectively) and decreases in slow frequencies (theta and delta; drowsiness, and sleep, respectively; Sanz-Martin et al., 2011). This pattern of increases in fast frequencies and decreases in slow frequencies are traditionally associated with cortical arousal and an activated state (Andreassi, 2000; Coult, 1998; Matousek & Petersen, 1983; Neidermeyer, 1998;;

Schwarz et al., 1981) and has been considered to be an index of arousal in both animals and humans (Hernandez-Gonzales et al., 2008; Sanz-Martin et al., 2011).

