EEG, Psychophysiology and Pupillary Response Acquisition - EEG and psychophysiology data will be collected using the BrainVision actiCHamp 64-channel, DC amplifier, 24-bit resolution, biopotential system. EEG data will be recorded with filters set at 1 and 30Hz, digitized at a sampling rate of 512Hz and stored on a computer using the PyCorder software. EEG data will be recorded to collect a 5-minute baseline measurement prior to administration of alcohol or placebo beverage. After beverage administration data will be collected for the duration of the emotion-regulation task (see below). To reduce confounding results due to artifacts, EEG signals will be examined for contamination by muscle activity and eye movement. Fast Fourier Transformation (FFT) analysis will be applied to 6-10 second epoch samples (corresponding to the delivery of stimuli) allowing for 1-s pre- and post-stimuli artifact subtraction with the spectral graph ranging from 0 to 30Hz at 0.5Hz-resolution. FFTs will be performed using EEGLab software to calculate 1) Absolute power (AP; power density of each frequency band expressed in microvolts squared; mV^2/Hz); 2) Relative power (RP; proportional contribution of each band to the total power across 1 – 30Hz). AP and RP will be transformed into Fisher's z-scores for statistical analyses. Skin conductance (SC) will be collected using the BrainVision GSR module with leads placed on the left index finger and left middle finger. SC will be recorded to collect a 5-minute baseline (as with EEG) measurement and for the duration of the emotion-regulation task and time-locked to evocative stimuli. SC data will be subjected to detrending and transformed to Fisher's z-scores for statistical analysis. Respiration and HRV will be measured using an integrated BrainVision respiration belt, and an EKG in Lead II position. As with EEG, baseline measures will be collected, and time locked to evocative events. EKG data will be quantified as respiratory sinus arrhythmia (RSA) which is a unique measure of parasympathetic activity and self-regulatory ability. Respiration and HRV data will also be transformed to Fisher's z-scores for statistical analysis. Pupillary response data will be collected using the EyeLink 1000 system high speed camera by SR Research (see sample data). Corneal reflection will be recorded at 250 Hz. The left and right pupil diameter measures will be averaged offline and baseline measures (1 sec prior to trial onset) will be subtracted. The difference between the maximum diameter during the trial and the baseline diameter will be calculated and transformed to Fisher's z-scores for statistical analysis. E-prime will control the flow of the emotion regulation task and generate timestamps to denote conditions for which all biopotential data can be analyzed.

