
Emotion Regulation Task - The proposed approach for studying emotion regulation has been used in several previous studies,⁶⁹ but we will utilize participant-tailored stimuli (video clips of partner's evocative behavior). During viewing, participants will be instructed to 1) experience the emotion they associate with the video (WATCH), or 2) to suppress the feeling of emotion (DON'T REACT). In the WATCH condition, participants will be instructed to let their

emotional experience occur naturally, and to pay attention to how they feel during the clip. In the DON'T REACT condition, participants will be instructed to attempt to suppress any feelings of emotion so as to prevent an observer watching physiological recordings from knowing that an emotional response has occurred. In both conditions, participants will be asked to indicate their corresponding emotional state using a slider (clicking and dragging with a mouse) on a continuous rating scale anchored by "very negative" (1) and "very positive" (100). A total of 50 unique video clips between 4 and 8 seconds in length will be used in the task; 25 evocative and 25 neutral. Each stimulus will be presented twice: once in the WATCH condition and once in the DON'T REACT condition. On each trial, participants will view a blank screen (1 second), fixation cross (1.5 sec), blank screen (.5 sec), the instruction (WATCH or DON'T REACT; 1.5 sec), the video clip (4-8 sec), and a blank screen (up to 2.5 seconds). The total amount of time required for the task will be approximately 25 minutes. Ratings obtained during the emotion regulation task will be averaged across stimulus type and regulation condition for the placebo and alcohol sessions for statistical analysis.

Participant Remuneration: Each participant will be paid \$20 per hour for their participation in the study. Each partner will have the opportunity to earn \$40 for his/her participation in the *Stimuli Acquisition Session* (\$80 total). The partner invited back for the *Emotion-Regulation Sessions* will have the opportunity to earn \$100 for his/her participation in the *Alcohol beverage Emotion-Regulation Session* and \$20 in the *Placebo beverage Emotion-Regulation Sessions* for a total of \$200 per couple. Participants will receive remuneration in the form of Visa or similar gift cards.

12) List of Appendices

Scale Purpose	Scale Name	Use/Source	α	Population

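### The 1–30 Hz EEG filter is set at recording rather than at analysis, which weakens the planned check for muscle activity in beta power

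*Combined protocol and SAP*

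**What the plan says.** The relevant text is in section 11 (Study Methods), under EEG, Psychophysiology and Pupillary Response Acquisition.

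- Recording: "EEG data will be recorded with filters set at 1 and 30Hz, digitized at a sampling rate of 512Hz", after which the data are stored. No unfiltered copy is mentioned and no filter roll-off is given.
- Equipment: "BrainVision actiCHamp 64-channel, DC amplifier, 24-bit resolution, biopotential system".
- Artefacts: "EEG signals will be examined for contamination by muscle activity and eye movement". No criterion, threshold, rejection rule, facial or neck muscle channel, or blinding of the person who marks artefacts is described.
- Analysis: the FFT uses epochs of 6–10 seconds, "allowing for 1-s pre- and post-stimuli artifact subtraction with the spectral graph ranging from 0 to 30Hz at 0.5Hz-resolution". Relative power is the "proportional contribution of each band to the total power across 1 – 30Hz".

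Section 4 (Background) describes the EEG arousal pattern: "alcohol is associated with increases in fast frequencies (beta and alpha; alertness and vigilance, and wakefulness, respectively", together with decreases in theta and delta.

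Under the Data Analysis Plan in section 14, Hypothesis 1b is the partner type by stimulus interaction, and Hypothesis 1c is the three-way interaction that adds beverage. The Aim 2 text adds the WATCH versus DON'T REACT factor but does not name its dependent variable.

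**The concern.** The plan sets the frequency range twice, once at recording and once at the FFT. The second limit is enough for the planned spectra. The first gains the analysis nothing and attenuates the signal above 30 Hz before anyone has looked for muscle activity.

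Muscle activity is broadband: part of it falls inside beta, and it extends well above 30 Hz, where it stands out from EEG. This is general EEG knowledge and does not come from the documents. After a 30 Hz recording filter the part inside beta stays in the data, while the part that would best reveal it is reduced or lost.

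This matters here because the stimuli are clips of the participant's own partner showing contempt, belligerence or criticism. A facial reaction to such clips could plausibly follow stimulus type, and could differ between DV and DNV partners. Section 11 itself expects conflict intensity to differ between the two couple types. Undetected muscle power in beta could then be read as cortical arousal.

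**Working it through.** The plan gives no figure for this point, so there is none to reproduce. It also gives no alpha, power, effect size, SD or contamination rate. Steps 2, 4 and 5 are therefore illustrations on stated assumptions.

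**1. Bandwidth.** The highest frequency that 512 Hz sampling can represent is 512/2 = 256 Hz. A 30 Hz limit leaves (256 − 30)/256 = 226/256 = 88% of that range unused. This describes lost bandwidth, not bias.

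**2. What the filter leaves above 30 Hz.** Assume a Butterworth low-pass filter of order k with its cut-off at 30 Hz. The power kept at frequency f is 1/(1 + (f/30)^(2k)). At 60 Hz this is 1/(1 + 2^(2k)):

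| Order k | Power kept at 60 Hz |
|---|---|
| 1 | 1/5 = 20% |
| 2 | 1/17 = 5.9% |
| 4 | 1/257 = 0.4% |
| 8 | about 0% |

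The loss runs from partial to essentially complete, depending on a roll-off that the plan does not state.

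**3. Which contrasts are exposed.** Let a(g,b,s) be the shift that muscle activity causes in the analysed EEG measure for group g, beverage b and stimulus s, and let d(g,b) = a(g,b,evocative) − a(g,b,neutral).

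- Bias in 1b: the mean over beverages of d(DV,b), minus the mean over beverages of d(DNV,b). It is non-zero when the stimulus-related artefact differs by group.
- Bias in 1c: [d(DV,alcohol) − d(DV,placebo)] − [d(DNV,alcohol) − d(DNV,placebo)]. If d depends on group but not on beverage, each bracket is zero and so is the bias. It is non-zero only if beverage changes the artefact differently in the two groups.

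For relative power, let B be beta power, R the power of the other bands and m the muscle power added in beta. The beta share becomes (B + m)/(B + R + m), which is larger. Any other band X becomes X/(B + R + m), which is smaller. Relative beta rises and relative alpha, theta and delta all fall. Three of these four changes match the arousal pattern in section 4; alpha moves the other way. In absolute power only beta changes.

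**4. Loss of detection.** A simulation used 400 clean and 400 contaminated single-channel epochs of 6 seconds at 512 Hz. The assumed EEG spectrum fell on average as 1/f², with variable slope, an alpha peak at 10 Hz and a beta peak at 20 Hz. Broadband muscle power was added, scaled to raise mean 13–30 Hz power by a set amount. The AUC for telling contaminated from clean epochs was:

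| Rise in beta | 40–100 Hz power | 20–30 Hz slope | Beta power alone |
|---|---|---|---|
| 10% | 0.95 | 0.73 | 0.60 |
| 25% | 0.99 | 0.85 | 0.69 |
| 50% | 1.00 | 0.92 | 0.80 |
| 100% | 1.00 | 0.96 | 0.90 |

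The last two columns represent a steep filter that leaves nothing usable above 30 Hz. A gentle one would do better. The values depend on the assumed spectra.

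**5. What an undetected shift would do.** Assume a two-sided 5% test, a normal approximation, no true effect, and a spurious shift of b SD. The rejection rate is Φ(δ − 1.96) + Φ(−δ − 1.96). For 1b, compare the evocative-minus-neutral difference between 112 and 112 partners, so δ = b/√(2/112). With b = 0.1, δ = 0.748 and the rate is Φ(−1.212) + Φ(−2.708) = 0.113 + 0.003 = 0.116. For a within-person contrast in all 224 partners, δ = b√224. That case covers 2a and 2b, and only if EEG power is analysed there.

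| Shift b (SD) | 112 vs 112 (1b) | Within-person, n = 224 |
|---|---|---|
| 0.05 | 7% | 12% |
| 0.1 | 12% | 32% |
| 0.2 | 32% | 85% |
| 0.3 | 61% | 99% |

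Nothing in the documents says which row, if any, applies.

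**The case against.** A reader might infer that muscle contamination cannot be detected at all. The documents do not support that. The plan commits to examining the signals, and bursts, the 64-channel scalp distribution and the in-band spectral slope all survive a 30 Hz filter. Large contamination would still be found fairly well (slope AUC 0.96 when beta doubles). The roll-off is unstated, so some signal above 30 Hz may remain, and the filter wording may be loose. This stands, and it limits the point to weaker detection, chiefly of small contamination.

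A reader might also infer that the artefact reproduces the study's arousal index. Beta is only one of the bands in that index, and alpha's relative share would move against the predicted direction. The filter is stated for the EEG data; skin conductance, RSA/HRV and pupil measures are not affected. This stands too.

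Section 14 argues that evocative stimuli are matched in arousal between the alcohol and placebo sessions. That protects 1c against an artefact driven by stimulus and group alone. It does not protect 1b, which averages over beverage.

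For Aim 2, one might read muscle artefact as false evidence of regulation. No EEG outcome is named there, and section 11 prepares the emotion ratings for analysis by stimulus and regulation condition. The direction is also unknown. Participants told to "attempt to suppress any feelings of emotion so as to prevent an observer watching physiological recordings from knowing" might relax the face or tense it.

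The edge correction does not answer the point. Clips last 4–8 seconds and epochs 6–10 seconds, which leaves 1 second on each side. The plan does not say how this would deal with a facial reaction during the clip itself.

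**Conclusion.** The point holds in a limited form. As written, the recording filter weakens the promised muscle check and gives nothing in return, since the FFT step already limits the spectrum. What remains exposed is absolute beta power and the relative-power shares, mainly in Hypothesis 1b.

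The size of any bias is unknown. The 88% figure is unused bandwidth and should not be read as a measure of harm. The AUCs and rejection rates show how the problem would behave under assumed spectra and assumed shifts; they do not estimate what happened in this study.

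The conclusion rests on three premises: that the filter acts on the stored data, as the text says; that muscle activity extends well above 30 Hz, which is outside knowledge; and that facial reactions to the clips can differ between DV and DNV partners, which is plausible but not documented. The change is worth making because it is cheap and because what a steep recording filter removes cannot be reliably recovered later.

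**What to change.** - Store EEG wide-band, with the upper limit set only by anti-aliasing. Apply the 1–30 Hz limit offline, after artefact detection that uses power above 30 Hz.
- Pre-specify the artefact criterion and rejection rule. Mark artefacts on files that carry a code only, without group, beverage or trial type.
- Report the rejected share of epochs by group, beverage, stimulus and instruction. That is 2 × 2 × 2 × 2 = 16 cells, with 25 epochs per participant for each stimulus and instruction in a session before rejection.
- State in the Aim 2 analysis whether EEG power is an outcome.
- If data were already stored with the 30 Hz filter, flag them in the analysis. If the filter was only ever applied offline, one sentence saying so settles the recording issue, but the artefact rule is still needed.

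The cost is a recording setting on the same equipment, a larger working bandwidth and slightly more processing.

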Psychophysiological Data - Psychophysiological data will initially be collected using laboratory computers. After each participant completes a laboratory procedure, the collected data will be transferred and saved to secure servers housed at the CTSC. Access to the servers is password protected and only authorized study personnel will be granted access.

Video Data - We request continued permission to keep the digital copies of the videos indefinitely because they contain significant clinical information that pertains to partner violence and because of that, impart significant scientific value. Blurring, distorting or destroying these videos would prevent us from accomplishing these goals and those of the current study. To ensure that the participant can make a fully informed consent regarding this, the consent form clearly states that the videotapes a) will show the participant's faces, b) will be kept indefinitely, and c) can and will be destroyed if the participant expressly requests that this be the case, which

is completely within their right. The digital videos will be delinked from identifying information, as described above. We understand that there is some question as to whether the videotapes themselves contain identifying information. Thus, increased caution must be imposed on the storage of these data. To this end, we will store the video data only in electronic form, on a different secured server than the rest of the study data, to prevent the implications of a potential server breach.

A master list of participant information and participant ID codes will be kept on a password protected computer in a locked room separate from any data collection computers (CTSC, [name]). The purpose of this is to be able to contact participants and schedule them for their subsequent study visits. This list will be destroyed at the conclusion of data collection for this study.

Data Analysis Plan: Preliminary analyses will be performed to ensure no violation of the assumptions of normality, linearity and homoscedasticity. Appropriate transformations (e.g. log transform of positively skewed data) will be performed prior to data analysis. Data will be analyzed according to the aims of the study.

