Specific Aim 1: To determine if normal increases in arousal after alcohol exposure is potentiated by evocative partner stimuli and is greater for DV partners compared to DNV partners. We will conduct a 2 (beverage condition: alcohol vs. placebo) x 2 (stimulus: evocative vs. neutral) repeated measures ANOVA with a between-subjects factor (partner type: DV vs. DNV). To test whether alcohol increases overall arousal (**Hypothesis 1a**), we will examine the main effect of alcohol vs. placebo on arousal variables, collapsing across partners and stimuli during the WATCH condition as alcohol should effect the arousal of both partner types equally. To test whether DV partners are more aroused by evocative partner displays than DNV partners (**Hypothesis 1b**), we will test the interaction effect of partner type and stimulus type, collapsing across alcohol and placebo conditions. Finally, to test the hypothesis that alcohol induced increases in arousal above placebo will be greater for evocative than neutral stimuli (**Hypothesis 1c**) for DV vs. DNV partners, we will test the three-way interaction in the 2 (DV vs. DNV) x 2 (alcohol vs. placebo) x 2 (evocative vs. neutral) repeated measures ANOVA. Specifically, this contrast will examine the effect of partner type when comparing stimuli type (evocative) to beverage condition (alcohol) on arousal and provides a critical control given that conflict intensity may differ between DV and DNV couples. The 3-way interaction (Hyp1c) will allow us to be able to determine whether the change in arousal between alcohol and placebo sessions for the evocative stimuli differs between couple types. The arousal level of evocative stimuli is matched between alcohol and placebo sessions, thus allowing for a controlled examination of alcohol-induced increases in arousal for evocative stimuli across DV and DNV couples.

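### Fisher's z is prescribed for physiological outcomes that are not correlations; if an ordinary z-score was meant, the unstated reference mean and SD can decide Hypothesis 1a

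*Combined protocol and SAP*

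**What the plan says.** Section 11 (Study Methods), under EEG, Psychophysiology and Pupillary Response Acquisition, gives the same instruction in four sentences:

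- EEG band power: "AP and RP will be transformed into Fisher's z-scores for statistical analyses". Absolute power is defined as "Absolute power (AP; power density of each frequency band expressed in microvolts squared; mV^2/Hz", and relative power as the "proportional contribution of each band to the total power across" the analysed frequency range. (The differing unit symbols may be a text-conversion artefact; nothing here rests on them.)
- Skin conductance: "SC data will be subjected to detrending and transformed to Fisher's z-scores for statistical analysis".
- Respiration and heart-rate variability, with the EKG quantified as respiratory sinus arrhythmia (RSA): "Respiration and HRV data will also be transformed to Fisher's z-scores for statistical analysis".
- Pupil: "The difference between the maximum diameter during the trial and the baseline diameter will be calculated and transformed to Fisher's z-scores for statistical analysis".

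No formula, mean, SD or unit of standardisation (trial, session, person, sample or baseline) is given. A five-minute recording before the beverage is planned, but it is not named as a reference for scoring.

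The Data Analysis Plan in section 14 adds a general rule: "Appropriate transformations (e.g. log transform of positively skewed data) will be performed prior to data analysis". It does not say how this fits with the Fisher's z instruction. For Hypothesis 1a the same plan states that "we will examine the main effect of alcohol vs. placebo on arousal variables, collapsing across partners and stimuli during the WATCH condition". Sections 8 and 11 put alcohol and placebo in separate sessions.

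**The concern.** Fisher's z is arctanh(x), designed to stabilise the variance of a correlation coefficient and real only for |x| < 1. The plan describes none of the listed outcomes as a correlation. The instruction covers every physiological arousal outcome, so it is not an isolated slip, and an analyst who follows it will meet values for which it has no result.

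The analyst must then substitute something. The likeliest candidate is an ordinary z-score, which needs a reference mean and SD. Beverage differs only between sessions, so any reference that centres each session separately subtracts the difference Hypothesis 1a is meant to estimate. Two analysts working in good faith from this text could reach opposite conclusions on Hypothesis 1a from the same data.

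**Working it through.** The documents state no effect size, SD, alpha or power, so there is no figure of the plan's own to reproduce. Two checks apply.

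**1. Where the named transform is defined.** Fisher's z = arctanh(x) = 0.5 × ln[(1 + x)/(1 − x)].

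- x = 0.05 gives 0.0500; 0.2 gives 0.2027; 0.5 gives 0.5493; 0.9 gives 1.4722.
- x = 1 gives infinity; x = 1.5, 5, 20 or −1.2 gives no real value.

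Relative power below 1 can therefore be transformed, and for small proportions the result is almost the input. For the other outcomes the result depends on the unit: a pupil change of 0.5 mm (an illustrative value) gives 0.549, while the same change written as 500 micrometres gives nothing.

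**2. What an ordinary z-score does to Hypothesis 1a.**

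*Algebra.* Centring on a session's WATCH trials makes the WATCH mean 0 in both sessions, so alcohol minus placebo is exactly 0 whatever the true effect. Suppose instead the reference is all trials in the session, half WATCH and half DON'T REACT (section 11: 50 clips, each shown under both instructions, so 100 trials). Then

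WATCH mean − session mean = 0.5 × (WATCH mean − DON'T REACT mean).

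Apart from division by the session SD, the beverage contrast becomes −0.5 × (alcohol × regulation interaction), with the interaction signed as the extra effect of alcohol under DON'T REACT. The alcohol main effect has dropped out.

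*Simulation.* From the documents: 224 participants (112 + 112), two sessions, two stimulus types, two regulation conditions, 25 clips per cell. Assumed, because the documents give no values: trial SD 1, person SD 1, session SD 0.5, alcohol effect 0.5, stimulus effect 0.3, regulation effect −0.2. There were 200 replicates, with a paired t-test on WATCH trials at the 5% level. With no alcohol × regulation interaction:

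| Reference for the z-score | Alcohol − placebo | Rejected |
|---|---|---|
| None (untransformed) | 0.496 | 100% |
| Within session, WATCH trials | 0 | 0% |
| Within session, all trials | −0.001 | 5% |
| Within person, both sessions | 0.417 | 100% |
| Whole sample | 0.325 | 100% |
| Pre-beverage baseline of that session | 0.522 | 100% |

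The whole-sample figure can be checked by hand. Total variance = 1 + 1 + 0.25 + 0.5²/4 + 0.3²/4 + 0.2²/4 = 2.345, so SD = 1.531 and 0.496/1.531 = 0.324. This is one linear rescaling of all the data, so it leaves the test statistics unchanged.

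With all trials in the session as reference, an interaction of +0.2 predicts −0.5 × 0.2 = −0.1 before scaling. The simulation gave −0.098, rejected in 100% of replicates with the wrong sign. An interaction of −0.2 gave +0.096.

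**3. What survives.** Within-session centring subtracts one constant from every cell of a session. It therefore cancels in any evocative-minus-neutral or WATCH-minus-DON'T REACT difference, and only the division by the session SD remains. A simulated alcohol × stimulus interaction of 0.20 came back as 0.192. Hypothesis 1c is the partner-type difference in that quantity; the three-way term itself was not simulated.

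**The case against.** The strongest reply is that the plan never mentions standardising within a session. A reader might infer that this is what Fisher's z-scores must mean, and that Hypothesis 1a is therefore zero by construction. The documents do not support that. They record a pre-beverage baseline and test a contrast that exists only between sessions, and neither fact points to within-session centring. Three other references fit the text equally well and keep the effect. Even under the within-session reading, the contrast is exactly zero only if WATCH trials are the reference. This reply stands: within-session scoring is one possible reading.

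A reader might also infer that most arousal outcomes would have no analysable value. That too goes further than the text, which gives no ranges for detrended skin conductance, RSA or pupil change. Failure depends on units and values, and relative power is computable. An undefined result would also show itself at the first run. It would not, however, tell the analyst what to use instead.

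Finally, a reader might take the general rule in section 14 as licence to choose a scale by its results. The text describes assumption checks and nothing more. Scale does matter for interactions in principle: multiplicative effects of 1.2 and 1.3 give 1.56 − 1.2 − 1.3 + 1 = 0.06 on the raw scale and 0 on the log scale. That is generic arithmetic, not evidence about this trial. What remains is that two transformation rules are unreconciled.

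**Conclusion.** The concern holds in limited form. The Fisher's z instruction is wrong as written for every physiological outcome: undefined at magnitude 1 or more and unit-dependent below that for absolute power, skin conductance, respiration, HRV/RSA and pupil change, and computable but without rationale for relative power. If an ordinary z-score was meant, the missing reference can move an assumed 0.5 effect on Hypothesis 1a from clearly detected (0.325 to 0.522) to 0, or to −0.098 with the wrong sign.

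The zero and the −0.5 multiplier are algebra; the other sizes rest on the assumed variances and effects. The exposure is confined to the alcohol main effect in the physiological outcomes. The tests of Hypotheses 1b, 1c and 2a to 2d all contain a within-session difference and largely survive the centring. The emotion slider ratings, which section 11 simply averages by stimulus and regulation condition, are outside the rule.

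**What to change.** Delete Fisher's z from all four sentences in section 11 and fix one scale per outcome before data are seen:

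- absolute power: log;
- relative power: a scale suited to proportions, such as logit;
- RSA: log, unless it is already in log units;
- respiration, detrended skin conductance and pupil change: raw units. Log is not an option for the last two, because a detrended signal or a difference from baseline can be zero or negative.

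If standardised units are wanted, use one mean and SD per outcome, pooled over both sessions and all participants, and never within session. State the window for detrending skin conductance as well: the plan does not give one, and a least-squares linear detrend over a whole session would itself set that session's mean to 0.

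In section 14, say that these scales take the place of the general transformation rule for these outcomes, and report the untransformed analysis as a sensitivity analysis. The cost is a few lines of wording and one extra set of model runs. No new data are needed.
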